2.10. Will health services research issues be addressed?

2.10.1 Economic evaluation

An economic evaluation is planned for Canadian centres. The economic hypothesis is that planned CS will be better for the twins, and less costly (as a result of fewer poor infant outcomes). The economic evaluation will, by adding a cost component to the evaluation of the interventions, enable decision and policy makers to judge the relative merits of one intervention over the other. A Ministry of Health perspective will be used.

The economic evaluation will involve determining resources consumed and unit prices for these resources. The estimates of unit prices will be combined with the resource use information for all trial participants. Resources consumed in either intervention in the Twin Birth Study will be collected in the clinical case report forms. The estimation of unit prices in this trial will be obtained from a sample of

Canadian participating centres. For the Twin Birth Study, this sample will consist of six hospitals (three smaller/community hospitals and three larger/teaching hospitals).

The unit price estimation within each hospital will involve two stages. First, estimates of professional fees for outpatient doctor visits, daily hospital visits, anaesthesia, and surgical operations will be obtained directly from each appropriate department/ministry of health (third party payer). Local health care experts will be asked to assist with the identification of the most appropriate fees for each service or course of treatment. Second, as existing per diem hospital rates are inadequate for detailed costing purposes, hospital cost models will be developed for each hospital. These models will be constructed with assistance and cooperation from hospital management and finance departments. The models will be designed to estimate department direct expenses, but will also include a share of hospital overhead expenses. Hospital unit price estimates which exclude hospital overhead costs may underestimate substantially the 'true' cost of hospital services. It is for this reason that considerable effort will be devoted to developing reliable and accurate hospital cost models.

2.10.2 Other health service research issues

The trial will examine women's health status, using SF-36, and satisfaction with method of delivery. In addition, women who report problematic incontinence will be asked to complete a short validated questionnaire about the impact of the incontinence: the IIQ-7 for urinary incontinence.⁵⁰

2.11. What is the proposed sample size and what is the justification for the assumptions underlying the power calculations?

We have estimated that the rate of perinatal or neonatal mortality or serious neonatal morbidity in the planned VB group will be approximately 4% of pregnancies. This estimate is based on the rates of adverse perinatal outcome associated with planned VB, found in the systematic review of studies which compared planned CS and planned VB for twins at \geq 32 weeks gestation,¹⁸ further review of studies of outcomes of twin births, and is consistent with the rates of perinatal mortality or serious neonatal morbidity among twins in Nova Scotia.²⁴ To further confirm the rate of the primary outcome in the planned VB group, we reviewed the Nova Scotia data (1988 to 2000) using the trial inclusion criteria in women who delivered twins at \geq 32 weeks gestation where the first twin presented as cephalic, to estimate the rate of primary outcome. The rate of the composite primary outcome was found to be 27/478 (6%) (95%CI: 4% to 8%) of pregnancies among women who had a vaginal delivery, or who had either an emergency CS or a CS in labour. We have decided to retain our conservative estimate of 4% for the purpose of calculating the sample size to allow for the possibility that the Nova Scotia data is an overestimate of the occurrence of the composite primary outcome in other centres, and we wish to be sure that the trial is of sufficient size to definitively answer the research question.

We wish the sample size to be adequate to find a reduction in risk of perinatal or neonatal mortality or serious neonatal morbidity from 4% to 2% with a policy of planned CS, if such a reduction exists, power = 80%, α error = 0.05 (2- sided). The sample size is thus 1250 pregnancies (or sets of twins) per group or a total N=2500. Since we will be treating each set of twins as a cluster in the analysis of the primary outcome, the power will be somewhat higher than 80% depending on the value of the correlation between members of the same twin pair.⁵⁵ The higher the correlation the less power will be increased. For a correlation of 0.9 the power is increased to 82% and for a correlation of 0.5 the power is increased to 91%. We expect the correlation to be high, and therefore we will require 2500 women and accept the slight increase in power. If we reduced the sample size based on a correlation that is too low, the power would be reduced.

The required sample size does not take into account the reduction in treatment effect caused by women changing their mind about method of delivery, between the time of randomisation and time of delivery. To allow for such crossovers, the required sample has been increased by approximately 10%, to a **total sample of 2800** (1400 women in each group). For the purposes of analysis, patients will be kept in their original randomised groups (intention to treat principle).

Based on our experience with the Term Breech Trial, we will assume a 20% loss to follow-up at 2 years. We estimate the rate of abnormal neurodevelopmental outcome in the planned VB group will be 2% (based on preliminary analysis [from September 2002] of the risk of abnormal neurodevelopmental assessment in the planned VB arm of the Term Breech Trial). A sample size of 2200 clusters of twins will provide >80% power for finding a reduction in risk of abnormal neurodevelopmental outcome from 2% to 0.5%, α error = 0.05 (2-sided).

We estimate the rate of problematic urinary/faecal/flatal incontinence at 2 years following delivery in the planned VB group will be 15% (based on preliminary analysis [from September 2002] of the risk of problematic incontinence in the planned VB arm of the Term Breech Trial). A sample size of 2200 women will provide >90% power for finding a reduction in risk of incontinence from 15% to 10%, α error = 0.05 (2-sided).

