2.8. What are the proposed outcome measures?

Because the trial interventions are aimed at managing the mother and her pregnancy, the outcomes are analysed for each set (or cluster) of twins (see section 2.11 for details).

2.8.1 Primary Outcome: Perinatal/neonatal mortality and/or serious neonatal morbidity.

(excluding lethal congenital anomalies)

In order to justify a policy of planned CS, which may increase the risks of maternal mortality and morbidity, there must be an important benefit for the infants. For each twin, perinatal/neonatal mortality and/or serious neonatal morbidity will be defined as one or more of the following during the first 28 days after birth:

- 1. Death (either as stillbirth or as a neonatal death 0 to 27 days after birth)
- 2. Birth trauma defined by any of the following:
 - a. Spinal cord injury
 - b. Basal skull fracture or depressed skull fracture
 - c. Long bone fracture (humerus, radius, ulna, femur, tibia or fibula)
 - d. Peripheral nerve injury (brachial plexus palsies, phrenic nerve palsy, facial nerve palsy) present at 72 hours of age (or at discharge from hospital if sooner)
 - e. Subdural or intracerebral haemorrhage of any kind (confirmed by ultrasound, computerised tomography [CT] scan, magnetic resonance imaging [MRI], or at autopsy)
- 3. Apgar score at 5 minutes less than 4
- 4. Abnormal level of consciousness:
 - a. Coma
 - b. Stupor or decreased response to pain
- 5. Neonatal seizures, defined as clonic movements which cannot be stopped by holding the limb, occurring on two or more occasions before 72 hours of age, regardless of cause
- 6. Need for assisted ventilation \geq 24 hours via endotracheal tube initiated within 72 hours after birth

- 7. Infection within 72 hrs after birth, defined by either of the following:
 - a. Septicemia (positive blood culture)
 - b. Meningitis (positive cerebrospinal fluid culture)
- 8. Necrotising enterocolitis (defined as either perforation of intestine, pneumatosis intestinalis or air in the portal vein) diagnosed by X-ray, surgery, or at autopsy
- 9. Broncho-pulmonary dysplasia (BPD): need for oxygen at a postnatal gestational age of 36 completed weeks + X-ray compatible with BPD
- 10. Intraventricular haemorrhage (IVH): Grade III or IV (diagnosed by cranial ultrasound or at autopsy)

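### Section 2.11 reuses per-pregnancy rates as per-twin rates, so the stated gain in power from clustering (to 82% or 91%) is really a small loss at both quoted correlations

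*Protocol*

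**What the plan says.** Section 2.11 of the protocol puts the primary outcome rate at a level that "in the planned VB group will be approximately 4% of pregnancies". It supports this with regional data, also counted per pregnancy: "27/478 (6%) (95%CI: 4% to 8%) of pregnancies". The target is a reduction "from 4% to 2% with a policy of planned CS" with 80% power and a two-sided 5% level, and the result is "The sample size is thus 1250 pregnancies (or sets of twins) per group or a total N=2500".

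The section then turns to the analysis of twin sets as clusters and states that "the power will be somewhat higher than 80% depending on the value of the correlation between members of the same twin pair". The figures follow: "For a correlation of 0.9 the power is increased to 82% and for a correlation of 0.5 the power is increased to 91" (per cent). It adds that a high correlation is expected and that the number of women will not be reduced on account of the gain.

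The outcome itself is defined at the level of the infant in section 2.8.1: "For each twin, perinatal/neonatal mortality and/or serious neonatal morbidity will be defined as one or more of the following". Section 2.16 plans cluster-trial methods for outcomes measured on both members of a pair. Nowhere does section 2.11 convert the pregnancy rate into a rate per twin.

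**The concern.** A pregnancy counts as affected when at least one twin is affected. Unless the two outcomes always coincide, the rate per twin is therefore lower than the rate per pregnancy. Moving from 1250 pregnancies to 2500 twins per group doubles the observations, but it also lowers the event rate and shrinks the absolute difference. The stated gain takes the first of these into account and leaves out the second.

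If so, the stated power is wrong in direction as well as in size, and readers are told that 2500 women give a surplus that does not exist. It also leaves unclear which quantity the 4% to 2% effect describes: it is labelled per pregnancy, while the planned analysis works on individual twins.

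**Working it through.** **Inputs.** From section 2.11: 4% vs 2% per pregnancy, two-sided 5% level, 1250 pairs per group, within-pair correlation (ρ) of 0.9 and 0.5. From sections 2.8.1 and 2.16: outcome per twin, cluster analysis.

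**Step 1: the base figure.** The usual two-proportion formula needs 1141 per group without a continuity correction and 1239 with it. Only the latter is close to the stated 1250. The corrected power is

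Φ{ [ |p1 − p2| − 1/n − 1.96·√(2·p̄(1−p̄)/n) ] / √([p1(1−p1) + p2(1−p2)]/n) }.

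At n = 1250, p1 = 0.04, p2 = 0.02: (0.0192 − 0.01337)/0.00681 = 0.855, so power is 80.4%. This matches the stated 80%.

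**Step 2: the plan's 82% and 91%.** Take 2500 twins per group with design effect 1 + ρ, and keep 4% and 2% as rates per twin.

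- ρ = 0.9: effective n = 2500/1.9 = 1316, power 82.5%.
- ρ = 0.5: effective n = 2500/1.5 = 1667, power about 90.7%.

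Both stated figures are reproduced, so the pregnancy rates were used as twin rates.

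**Step 3: convert the rates.** With equal risk p for both twins, the chance that at least one is affected is

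P = 2p − [p² + ρ·p(1−p)].

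Solve for P = 4% and P = 2%:

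- ρ = 0.9: p = 3.65% and 1.82%.
- ρ = 0.5: p = 2.69% and 1.34%. Check: 0.05382 − 0.00072 − 0.5 × 0.02619 = 0.0400.

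**Step 4: power at the converted rates**, same formula and same effective n:

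| | Pregnancy level | Twins, ρ = 0.9 | Twins, ρ = 0.5 |
|---|---|---|---|
| Stated in 2.11 | 80% | 82% | 91% |
| 1250 pairs, continuity-corrected | 80.4% | 78.7% | 75.6% |
| 1250 pairs, uncorrected | 83.5% | 82.0% | 79.3% |
| 1400 pairs, continuity-corrected, before crossover | 84.9% | 83.4% | 80.6% |

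A formula on the log odds ratio gives 82.0%, 80.5% and 77.7% for 1250 pairs. A simulation of an uncorrected cluster-robust test gave about 82–83% and 80%, against 84% for the pregnancy-level test. Under each method the twin-level power lies below the pregnancy-level power.

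**Step 5: the reverse reading.** If 4% and 2% were meant per twin, the implied pregnancy rates are:

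- ρ = 0.9: 0.08 − 0.0016 − 0.9 × 0.0384 = 4.4%, and 0.04 − 0.0004 − 0.9 × 0.0196 = 2.2%.
- ρ = 0.5: 0.08 − 0.0016 − 0.5 × 0.0384 = 5.9%, and 0.04 − 0.0004 − 0.5 × 0.0196 = 3.0%.

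These are not the stated 4% and 2%. At ρ = 0.5 the control rate is also almost the 6% against which the plan calls 4% conservative.

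**The case against.** The best defence is that nothing in the design rests on the faulty figures. The 1250 per group is a pregnancy-level number, and section 2.11 expressly declines to trade the supposed gain for fewer women. The authors expect a high correlation, and at 0.9 the gap is only 82% against 79%. The 15-point gap at 0.5 belongs to a case they do not expect. All of this stands, and it limits the consequence.

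The corrected level also depends on a convention that the protocol does not name. Without the continuity correction, power at 0.9 comes to 82.0%, which happens to equal the stated figure. That does not rescue the claim: the uncorrected base is 83.5%, so power still falls, and the plan's own calculation would then have read 85.3% and 92.3%.

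Four stronger conclusions are tempting, and the documents do not support them.

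- **That the trial is underpowered.** Whether 1250 pairs fall short of 80% depends on the convention and the correlation. What is robust is the loss against the pregnancy-level comparison.
- **That clustering lowers power at every correlation.** Near zero it does not: the corrected figure is 80.5% at ρ = 0.01 and 80.7% at ρ = 0, against 80.4%.
- **That the allowance for crossover is already spent.** Section 2.11 gives no crossover rate from which this could be computed.
- **That the primary outcome should become either twin affected.** This would change the planned analysis, and correcting the power statement does not require it.

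Finally, the conversion assumes equal risk for both twins, while section 1.1.3.1 cites a relative risk of 2.1 for the second-born. The exact figures would move under unequal risk, so the assumption has to be stated.

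**Conclusion.** The point holds as a unit error in a descriptive power statement. With the rates as labelled, per pregnancy, the stated powers are too high by about 3 points at correlation 0.9 and 15 points at 0.5 (continuity-corrected), and the stated direction is wrong at both. Relative to the pregnancy-level comparison, the loss is about 1.5 to 2 points at 0.9 and 4 to 5 points at 0.5 under the corrected and uncorrected formulas.

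This rests on three assumptions: a pregnancy counts as an event if at least one twin is affected, both twins have the same risk, and the correlation is the same in both arms. No reading of sections 2.8, 2.11 and 2.16 reconciles the text. If the pregnancy were the unit of analysis, each pair would give one observation and the within-pair correlation would add no power. If 4% were per twin, the label and its supporting data would be in the wrong unit. The practical harm is limited to a misstated power and an unclear effect unit.

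**What to change.** Do one of the following in section 2.11.

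- **If the rates are per pregnancy, as written:** delete the claim that power rises. State that, with at least one twin affected in 4% vs 2% of pregnancies, equal risk for both twins and the same correlation in both arms, 1250 pairs per group give about 79% power at correlation 0.9 and 76% at 0.5 with a continuity correction, or 82% and 79% without. Add that 1400 pairs give about 83% and 81%, continuity-corrected and before any crossover.
- **If the rates were meant per twin:** correct the unit, keep 82% and 91%, and give the implied pregnancy rates (about 4.4% and 2.2% at 0.9, 5.9% and 3.0% at 0.5). Then revisit the comparison with the regional 6%, which is per pregnancy.

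In either case, add one line in section 2.8 or 2.16 saying whether the 4% to 2% effect is per twin or per pregnancy, so that it matches the planned cluster analysis.

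The cost is a few sentences and, on the first route, a less favourable power statement. Neither the number of women nor the primary analysis changes.

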2.12. What is the planned recruitment rate?

We undertook *a pilot study*⁵⁶ to ascertain the willingness of women to join the Twin Birth Study. Sixty-four pregnant women with twins were asked to read a patient information sheet and consent form prepared for the Twin Birth Study and to indicate their willingness to participate. Of the 64 women interviewed, 48% said they would be willing to take part in the Twin Birth Study.

We plan to recruit from Canadian centres as well as centres in other countries that are committed to answering this important question and can comply with all aspects of the study protocol. We estimate that approximately 2% of all pregnancies will be twin pregnancies, and that approximately 25% of these will be approached and eligible for the study. Although recruitment rates will vary from one centre to another, we have estimated that the recruitment rate will be on average 30% of eligible twin pregnancies. This estimate is based on the results of our *pilot study*⁵⁶ and our experience in the Term Breech Trial, where 20% of women estimated to be eligible agreed to take part. Thus, on average, we anticipate that 0.15% of all births in a centre will participate (for a centre with 4000 births per year, this would be 6 recruits per year). We plan to enrol 2800 women over 4.5 years. Allowing for gradual increases in enrolment over the first 2 years (400/yr, 650/yr, and then 700/yr thereafter) we estimate that we will need 100-150 centres, depending on their size, referral pattern and ability to recruit. To recruit 700/year, we will need centres with approximately 470,000 births per year.

2.13. Are there likely to be any problems with compliance?

Based on our experience with the Term Breech Trial, we do not anticipate problems with compliance. However, we will check compliance with mode of delivery quarterly for the trial as a whole and by centre. If problems occur, we will work with the centres to resolve them.

2.14. What is the likely rate of loss to follow up?

In the Term Breech Trial, we recruited 2088 women from 121 centres world-wide and only 5 women were lost to follow-up for the primary outcomes. The Twin Birth Study follows a similar protocol to that of the Term Breech Trial and thus we anticipate virtually complete follow-up for the primary outcome. The follow-up to 2 years will be more difficult but based on the ongoing follow-up of the Term Breech Trial, we anticipate a follow-up rate of 80%.

2.15. How many centres will be involved?

We have received confirmation from over 120 centres (representing over 470,000 births per year) that they are willing to join the study. The majority of these centres have contributed successfully to our previous and ongoing trials. Due to the large sample size, international collaboration will be required.

2.16. What is the proposed type and frequency of analyses?

Analyses of outcomes measured on both members of each twin pair will be those appropriate for a stratified cluster randomised trial.⁵⁷

Interim analyses: There will be two interim analyses: the first after complete data have been received on the first 1000 women recruited to the study and the second after complete data have been received on

the first 1800 women recruited. Baseline data, data describing the compliance with the intervention and the primary outcome data will be presented in tabular form, using an intention to treat approach, masked to allocation group, to an independent DSMB. If the difference between groups in the primary outcome is different at p < 0.002 (2 sided), the trial will be stopped; otherwise recruitment will continue until the full sample size has been accrued.

Final analysis: An intention to treat approach, which includes all mothers and fetuses as randomised, will be used. Descriptive statistics (means, standard deviations, proportions) will be calculated to check for any major dissimilarities in the study groups with regard to patient demographics and other baseline information. Methods proposed by Donner and Klar⁵⁷ will be used to compare the rates of the primary outcome, perinatal/neonatal mortality and/or serious neonatal morbidity between the two study groups controlling for the stratification variables (parity $[0, \ge 1]$, gestational age at randomisation $[32^{0/7}-33^{6/7}]$ $34^{0/7}$ - $36^{6/7}$, $37^{0/7}$ - $38^{6/7}$ weeks]) and other prognostic factors (maternal age [<30, \ge 30 years], presentation of twin B at randomisation [cephalic, non-cephalic], chorionicity ⁵⁸ [dichorionic, monochorionic[§]], and the country's national perinatal mortality rate (PMR) (per 1000) as reported by the World Health Organisation ⁵⁹ [<15, 15-20, >20]). Mixed effects models will be used to determine if treatment effects vary between centres and to test for interactions between prognostic factors and treatment. A similar analysis will be performed for the neurodevelopmental outcome. Logistic regression will be used to compare the rates of problematic incontinence at 2 years between groups, controlling for prognostic factors. The level of statistical significance for the analysis of the primary and secondary outcomes will be p < 0.05 (two-sided). Adjusted odds ratios and 95% confidence intervals will be calculated to determine the magnitude of the association between the two study groups and the primary and secondary outcome measures. The number of additional CS needed (number needed to treat) to prevent one adverse outcome will also be calculated.

We will use logistic regression to calculate the adjusted odds ratios and 95% confidence intervals for the comparison of the two study groups with respect to the rates of the following other outcome measures: problematic incontinence at 3 months, satisfaction with the birth experience, depression, and breast feeding. The two study groups will be compared with respect to quality of life (SF-36) using a repeated measures ANOVA. The level of statistical significance for the analysis of the other outcomes will be p < 0.01 (two-sided).

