1.2. What are the principal research questions to be addressed?

1.2.1 Primary Research Question:

For twin pregnancies of $32^{0/7}$ - $38^{6/7}$ weeks gestation, where twin A is presenting cephalic, does a policy of planned CS decrease the likelihood of perinatal or neonatal mortality or serious neonatal morbidity, during the first 28 days after birth, compared to a policy of planned VB?

1.2.2 Secondary Research Questions:

a) For twin pregnancies of $32^{0/7}$ - $38^{6/7}$ weeks gestation, where twin A is presenting cephalic, does a policy of planned CS compared to a policy of planned VB decrease the risk of death or poor neurodevelopmental outcome of the children at 2 years of age, corrected for gestational age at birth?; b) For twin pregnancies of $32^{0/7}$ - $38^{6/7}$ weeks gestation, where twin A is presenting cephalic, does a policy of planned CS compared to a policy of planned VB decrease the risk of problematic urinary or faecal/flatal incontinence for the mother at 2 years postpartum?

1.2.3 Other Research Questions:

For twin pregnancies of $32^{0/7}$ - $38^{6/7}$ weeks gestation, where twin A is presenting cephalic, does a policy of planned CS compared to a policy of planned VB decrease or increase maternal death or serious maternal morbidity (occurring up to 4 weeks following the birth)?; maternal satisfaction with method of delivery determined at 3 months postpartum?; maternal quality of life at 3 months and 2 years postpartum?; maternal depression at 3 months and 2 years postpartum?; breast feeding at 3 months postpartum?; problematic urinary or faecal/flatal incontinence for the mother at 3 months postpartum?; and costs?

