2.8.3.1 Maternal death or serious maternal morbidity

This is defined as one or more of the following during pregnancy, labour, birth or within the first 28 days following the birth: death; haemorrhage (documented blood loss of \geq 1500cc, blood transfusion required, or need for dilatation/curettage after delivery); laparotomy; genital tract injury (hysterectomy,

vulvar or perineal haematoma requiring evacuation, broad ligament haematoma confirmed by ultrasound, CT or MRI, intraoperative damage to bladder, ureter or bowel requiring repair, fistula involving the genital tract, 3rd or 4th degree perineal tear involving the anal sphincter and/or mucosa); thromboembolism (deep vein thrombosis, thrombophlebitis, or pulmonary embolism) requiring anticoagulant therapy; systemic infection (temperature of 38.5° C or more on 2 occasions at least 24 hours apart not including the first 24 hours, or pneumonia [confirmed by X-ray], or sepsis [confirmed by blood culture]); major medical life threatening illness (eg adult respiratory distress syndrome, amniotic fluid embolism, disseminated intravascular coagulation, bowel obstruction, paralytic ileus [requiring naso-gastric suctioning]); wound infection (requiring prolongation of hospital stay, readmission to hospital or repeated treatment as an outpatient), wound dehiscence or wound breakdown, or other serious maternal complication.

2.8.3.2 Maternal satisfaction with method of delivery:

Determined by the mother's willingness to have the same method of delivery again or recommend it to a friend

- 2.8.3.3 Maternal quality of life: measured by the SF36 51,52
- 2.8.3.4 Maternal fatigue: measured by the Multidimensional Assessment of Fatigue Scale 53
- 2.8.3.5 Maternal depression: measured by the Edinburgh Postnatal Depression Scale ⁵⁴ A score of >12 will indicate depression
- 2.8.3.6 Problematic urinary or faecal/flatal incontinence at 3 months: Women who report problematic incontinence will be asked to complete additional validated questions about the impact of the incontinence, using the IIQ-7.⁵⁰
- 2.8.3.7 Breast feeding

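### Repeated measures ANOVA for SF-36, in its usual complete-case form, leaves out women missing either visit, although the protocol expects 20% loss at 2 years

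*Protocol*

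**What the plan says.** - Section 1.2.3 lists among the other research questions "maternal quality of life at 3 months and 2 years postpartum". Section 2.8.3.3 names the instrument: "Maternal quality of life: measured by the SF36". Sections 2.7 and 2.9 collect it by questionnaire at those two times. No baseline SF-36 is described.
- Section 2.16, final analysis: "The two study groups will be compared with respect to quality of life (SF-36) using a repeated measures ANOVA". Other outcomes, SF-36 among them, are tested at p < 0.01 (two-sided).
- The same part of 2.16 begins: "An intention to treat approach, which includes all mothers and fetuses as randomised, will be used". It names mixed effects models too, but only for variation of the treatment effect between centres and for interactions with prognostic factors.
- Section 2.11: "we will assume a 20% loss to follow-up at 2 years". Section 2.14 agrees: "we anticipate a follow-up rate of 80" per cent. No response rate is given for the 3-month questionnaire.
- Section 2.11 sets the randomised sample at 2800, that is "1400 women in each group".

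**The concern.** With two visits, the group test in a classical repeated measures ANOVA is a test on each woman's mean of her two scores. A woman without a 2-year score has no such mean and drops out, together with the 3-month score she did supply. The protocol thus pairs a method that usually needs both visits with its own forecast that one woman in five will lack the second, while stating that all mothers are analysed as randomised.

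Two things are at stake. The first is precision, mostly at 3 months, because data already collected are not used. The second is possible bias: if loss depends on the 3-month score, and differently in the two arms, the women with both scores are no longer comparable between arms. The observed 3-month score could correct for that, but a complete-case analysis ignores it for the women who are lost.

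**Working it through.** **The plan's own figures.** Retention at 2 years: 2800 × 0.80 = 2240, against 2200 used in section 2.11, a difference of 1.8%. For that number the protocol states: "A sample size of 2200 women will provide >90% power for finding a reduction in risk of incontinence from 15% to 10" per cent. With 1100 per group, two-sided α = 0.05 and 15% against 10%, the normal approximation gives 94.4%, which agrees. No sample size or power is given for SF-36, so that comparison has no figure to reproduce.

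**Records discarded.** Lost at 2 years: 2800 × 0.20 = 560. How many of these women gave a 3-month score depends on r, the 3-month response, which is assumed here to lie between 80% and 100%.

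| r | 3-month scores observed | Discarded, if 3-month non-responders are all among those lost at 2 years | Discarded, if the two losses are independent |
|---|---|---|---|
| 100% | 2800 | 560 | 560 |
| 90% | 2520 | 2520 − 2240 = 280 | 2520 × 0.20 = 504 |
| 80% | 2240 | 2240 − 2240 = 0 | 2240 × 0.20 = 448 |

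The range is 0 to 560, and 560 is the upper end. Women with both scores number 2240 at most, and 2240 × 0.80 = 1792 at r = 80% with independent losses.

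**Precision.** Take r = 100%, equal variances at the two visits, between-visit correlation ρ (assumed 0.3, 0.5, 0.7) and 80% observed at 2 years in each arm. The ratio of the complete-case standard error to that of a likelihood fit on all scores is:

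- 3-month contrast: √(1/0.8) = 1.118, whatever ρ.
- Two-visit average: √(2/(1.8 − 0.2ρ)) = 1.072, 1.085, 1.098.
- 2-year contrast: 1/√(1 − 0.2ρ²) = 1.009, 1.026, 1.053.

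The loss is therefore about 12% at 3 months, 7-10% for the average and 1-5% at 2 years. A lower 3-month response that overlaps with the 2-year loss shrinks all three.

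**Bias.** Simulation with 1400 women per arm, complete 3-month scores, ρ = 0.5 and about 20% loss at 2 years. Loss depends on the 3-month score through an assumed log-odds slope per SD. The estimate is the group difference in the two-visit average, in SD units.

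| Dependence of loss on 3-month score | True effect | Complete cases | All scores, likelihood |
|---|---|---|---|
| None | 0 | 0.00 | 0.00 |
| Slope 0.3 or 0.8, same in both arms | 0 | 0.00 | 0.00 |
| Slope 0.3, same in both arms | 0.2 | 0.198 | 0.20 |
| Slope 0.8, same in both arms | 0.2 | 0.186 | 0.20 |
| Slope 0.3, one arm only | 0 | 0.045 | 0.00 |
| Slope 0.5, one arm only | 0 | 0.08 | 0.00 |
| Slope 0.8, one arm only | 0 | 0.12 | 0.00 |

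Loss that depends on the score equally in both arms causes no bias when there is no effect, and only slight attenuation when there is one. Material bias needs a difference between arms. The slopes are illustrative; nothing in the protocol fixes them.

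**The case against.** The strongest reply is that the protocol nowhere says incomplete women are excluded. Repeated measures ANOVA can be read as the name of a design, a likelihood fit under that name keeps every woman with at least one score, and the handling of a missed visit is commonly left to the SAP. This stands in part: deletion is an inference from the usual meaning of the method. It is a reasonable inference, because section 2.16 uses the term mixed effects models separately and for other purposes. The criticism is of a method that the protocol names, not of a missing detail.

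A reader might infer three stronger things that the document does not support.

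- That the comparison is unbiased only if loss is completely at random. The simulation shows otherwise: score-related loss that is alike in both arms leaves the group difference unbiased under no effect. Lack of masking and a large number of centres make differential loss possible, not established.
- That 560 discarded scores and a 12% wider interval are expected values. Both need complete 3-month response, and the 12% applies to the 3-month contrast only.
- That the ANOVA can answer only an averaged question. It can contain a group-by-time term and contrasts at each visit, and the protocol does not limit reporting to the overall group test.

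It is also true that with two visits sphericity is not an issue, so on complete data the ANOVA and a mixed model give essentially the same group and interaction tests. The whole difference lies in the treatment of missing scores.

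**Conclusion.** The point holds in a limited form. The named method, in its usual form, does not fit the protocol's own forecast of follow-up or its statement that all mothers are included. The number of discarded 3-month scores lies between 0 and about 560 of 2800. The precision losses above are maxima, resting on complete 3-month response and an assumed correlation of 0.3 to 0.7. Any bias depends mainly on loss patterns differing between arms and cannot be sized from the protocol.

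The importance is modest. SF-36 is one of several other outcomes, tested at p < 0.01, with no sample size resting on it. No primary or secondary conclusion changes. The change is still worth making, because the alternative is at least as precise, is more robust to missing visits and costs almost nothing.

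**What to change.** In section 2.16, replace the repeated measures ANOVA with a likelihood-based linear mixed model using all available SF-36 scores. Its terms are group, visit, group-by-visit and the stratification factors (parity and gestational age at randomisation), with an unstructured covariance between the two visits. State that the group difference will be reported at 3 months and at 2 years, each with a confidence interval. If a likelihood fit was intended all along, the same sentence settles it.

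The model corrects for loss that is explained by the observed 3-month score and the covariates. It does not correct for loss that depends on the unseen 2-year score, so a short sensitivity analysis for that case is a sensible addition.

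The cost is one sentence of text. The data collected, the sample size and the visits are unchanged, and standard software fits the model.
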